Similarly, we will send recruitment letters and study information sheets to patients at high outlier facilities. We will attempt up to 5 or 6 attempts per patient, including leaving voice mails and providing call-back information. We will attempt to interview 1-2 patients from each site, with no more than 15 interviews total. If patient response from some sites is insufficient, we will increase the number of patients interviewed at each site to up to 4 and/or send recruitment letters and study information sheets to patients at additional high outlier sites. We will continue in this manner until all 15 patient interviews are complete or until we feel we have reached saturation, whichever comes first. Patients will be mailed a \$20 gift card following their completion of the interview.

We will pilot provider interviews with study consultants. Pilot interviews will be conducted by phone and in person and will NOT be audiotaped. We will also obtain feedback on the patient interview guide from CCMR's Veteran Research Engagement Council (VREC). We will refine the draft semi-structured interview guides for providers and patients to elicit beliefs and attitudes regarding starting and stopping ADT as localized prostate cancer treatment, as well as informed decision-making preferences, and to ensure it can be completed in a timely fashion. Interview guides are developed iteratively - questions are developed, tested, and then refined based on what one learns from asking participants these questions. However, any substantial change or addition to interview guide questions will be submitted to the IRB for approval.

Semi-structured interviews with both patients and providers will be recorded using the Olympus DS-7000 DVR so that authorized study staff can turn the interview responses to written text to help identify common themes. Each phone interview will last approximately 30 - 45 minutes. Please note that we will ask permission to record interviews. After each interview, the audio file of the recording will be uploaded to a restricted folder located on a secure VA computer server protected behind the VA firewall. Only authorized study staff will have access to this folder. Once the interview information is located on the VA server, the original interview recording will be deleted from the recording device according to VA policy.

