Interview data will be transcribed, coded and entered into NVivo software for analysis. We will use a preliminary coding scheme based on the Theoretical Domains Framework (TDF) and prior work by Huijg and Birken consisting of a three step process including: 1) coding affirmative and negative utterances regarding ADT use as localized treatment into TDF domains, 2) collecting responses across respondents into themes, 3) tallying the total number of mentions per theme, as well as conflicting beliefs within a theme (e.g., ADT is good vs. ADT is bad), according to the TDF domains, with particular emphasis on those included in our conceptual model. This qualitative work will inform Aim 2 and gather rich information for our proposed pilot intervention strategies.

We will provide a summary of results to participating providers and patients upon request once results are available. These summaries will contain only aggregate data and/or broad summaries and will be submitted to the IRB for approval prior to dissemination.

All research data will be de-identified at the termination of the study, if not sooner. Study data will be moved to the VA CCMR data repository and destroyed by the CCMR data manager six (6) years following the end of the Fiscal Year after completion of the research project as described in the VA Records Control Schedule.

AIM 2:

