The goal of Aim 2 is to then prioritize barriers and facilitators to de- implementation of chemical castration with ADT discovered in Aim 1. The highest priority barriers will need to be addressed during strategy development and tailoring for our pilot interventions in Aim 3 to support acceptability and feasibility in practice. We will accomplish this using a discrete choice experiment (DCE), a method in which respondents (urologists) react to hypothetical choice sets based on a combination of attributes (characteristics of the product under study, in this case the approach to de-implementing ADT) and levels (descriptors of each attribute). In our DCE, the barriers and themes with the highest frequency and most conflicting beliefs across respondents identified in Aim 1 will be refined and presented as the "attributes" and associated levels will be developed. In short, we will use data obtained from Aim 1 to develop TDF-based choice sets for inclusion in a national urologist discrete choice experiment. Once we have the most important, not just most common or conflicting, themes and barriers based on a national urologist DCE, we can select the most effective evidence-based behavior change techniques to direct de-implementation tailoring efforts in Aim 3. Marketing expert [name] (Co-I) will align our efforts with state-of-the-art discrete choice and marketing practices.

AIM 3:

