8 DATA ANALYSIS

AIM 1:

Interview data will be transcribed, coded and entered into NVivo software for analysis. We will use a preliminary coding scheme based on the Theoretical Domains Framework (TDF) and prior work by Huijg and Birken consisting of a three step process including: 1) coding affirmative and negative utterances regarding ADT use as localized treatment into TDF domains, 2) collecting responses across respondents into themes, 3) tallying the total number of mentions per theme, as well as conflicting beliefs within a theme (e.g., ADT is good vs. ADT is bad), according to the TDF domains, with particular emphasis on those included in our conceptual model. This qualitative work will inform Aim 2 and gather rich information for our proposed pilot intervention strategies.

AIMS 2:

Discrete choice experiments are based on Random Utility Theory which assumes participants will select responses with the most personal utility.^{80,83} Because respondents respond to a variety of choice sets, we will be able to estimate the relative priority of our barrier attributes and their levels. We will model urologists stated preferences providing quantitative information about the relative value, or utility, providers place on barrier attributes such as *physician autonomy* or *clinical time*, for example, using the equations below. There are ~250 urologists on the listserv. If 50% respond: 125 surveys with ~5 scenarios – 625 scenarios x 5 attributes = 3125 data elements for analysis. [name] is an expert in multi-level and multinomial regression techniques and will conduct the analyses with direction from Drs. [name] and [name] given their DCE expertise. Our methods will adjust for dependency of responses within individuals as they respond to different choice sets and will be modeled after published DCEs according to the following example equation:

Utility = (Constant) + β_1 (e.g., physician autonomy) + β_2 (e.g., clinical time) ...

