9 QUALITY CONTROL AND QUALITY ASSURANCE

AIM 1:

Interviews will be audiotaped and transcribed verbatim for content. We will conduct analyses concurrently with ongoing interviews, if timing permits, to inform subsequent data collection and analysis. We will use a preliminary coding scheme based on the TDF and prior work by Huijg et al.,⁴¹ and Birken et al.,⁷⁶ consisting of a three step process including: 1) coding affirmative and negative utterances regarding ADT use as localized treatment into TDF domains, 2) collecting responses across respondents into themes (e.g., "ADT prevents cancer spread" into a 'ADT is beneficial' theme, "urologists should be able to treat patients as they wish" into a 'Physician autonomy' theme), 3) tallying the total number of mentions per theme, as well as conflicting beliefs within a theme (e.g., ADT is good vs. ADT is bad), according to the TDF domains, with particular emphasis on those included in our conceptual model. Study interviewers and qualitative analysts will both independently review and code transcripts and meet regularly to compare coding results until reaching agreement on code definitions and establish the reliability of the coding process (>80% simple agreement). During this process, study investigators and interviewers will also meet to categorize the codes into TDF domains, identify emerging themes, and document ongoing data interpretation in memos. Once data are coded, we will use QSR NVivo software to organize the data. Drs. [name] and the research team will meet regularly to discuss code summaries and memos, developing findings with a focus on informing the Aim 2 discrete choice tool. At the end of this aim we will have identified the highest frequency themes and themes with conflicting provider and patient beliefs across TDF domains for de-implementing ADT.

AIMS 2 AND 3: tbd

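### The Aim 1 interview guide may change during fielding, but themes are scored by total mentions with no account of who was asked, so a barrier added late may be ranked too low for the discrete choice experiment

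*Combined protocol and SAP*

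**What the plan says.** Four parts of the combined protocol and SAP bear on this.

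- **The guide can change.** Section 6 (Aim 1): "Interview guides are developed iteratively - questions are developed, tested, and then refined based on what one learns from asking participants these questions". The control on this is ethical review: "any substantial change or addition to interview guide questions will be submitted to the IRB for approval".
- **Analysis can steer later interviews.** Section 9 (Aim 1): "We will conduct analyses concurrently with ongoing interviews, if timing permits, to inform subsequent data collection and analysis".
- **Themes are scored by totals.** Sections 6, 8 and 9 give the same three-step coding, which ends in "tallying the total number of mentions per theme, as well as conflicting beliefs within a theme". What is coded is utterances in general: "coding affirmative and negative utterances regarding ADT use as localized treatment into TDF domains".
- **The score feeds the DCE.** Section 6 (Aim 2) takes as attributes "the barriers and themes with the highest frequency and most conflicting beliefs across respondents identified in Aim 1", to be refined before use. Section 8 plans on 5 attributes.

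Interviews stop at 20 providers and 15 patients, or sooner at saturation. The documents describe no log of guide versions, no count of respondents asked each question, no point at which the guide is frozen, and no re-coding of early transcripts.

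**The concern.** A question added after interview k is put only to later respondents. A raw total then mixes two things: how common a belief is, and how long its question was in the guide. Themes discovered through iteration are the ones at a disadvantage. The same holds for conflicting beliefs, since fewer people asked means fewer chances for disagreement to appear.

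This matters because the total is used to select. Section 6 (Aim 2) wants the DCE to find the barriers that matter most and not merely the commonest, but a DCE estimates importance only for the attributes it contains. A barrier ranked too low in Aim 1 may never be weighed there. IRB review governs whether a question may change. It does not govern how answers are counted afterwards.

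**Working it through.** The plan states no error rate or sample-size argument for theme selection, so there is no figure of its own to reproduce. The one related calculation, in Section 8, is consistent: 250 × 50% = 125 surveys; 125 × 5 = 625 scenarios; 625 × 5 = 3125 data elements. It supplies the planning figure of five attributes.

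**Inputs from the documents:** N = 20 provider interviews (maximum); five attribute places.

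**Assumptions (the documents give none of these):** at most one count per respondent; barrier A raised by 60% of those asked about it; barrier B raised by 40% and asked throughout; A's question added after interview k; a share q of respondents raising A before it is asked about.

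**Step 1: expected count.** As a fraction of what A would score if asked throughout, with r = q / 0.60, the expected count is [(N − k) + k·r] / N.

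- r = 0: k = 5, 10, 15 give 15/20 = 75%, 10/20 = 50%, 5/20 = 25%.
- r = 0.5 (q = 30%): 17.5/20 = 87.5%, 15/20 = 75%, 12.5/20 = 62.5%.

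The fraction is below 1 whenever r < 1, that is, whenever asking raises mentions.

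**Step 2: chance of A scoring below B.** A ~ Bin(20 − k, 0.60) + Bin(k, q) and B ~ Bin(20, 0.40), independent. Exact P(A < B), ties excluded:

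| Question added after | q = 0% | q = 10% | q = 30% | q = 40% | Share of those asked |
|---|---|---|---|---|---|
| start (k = 0) | 0.07 | 0.07 | 0.07 | 0.07 | 0.07 |
| interview 5 | 0.30 | 0.25 | 0.16 | 0.13 | 0.11 |
| interview 10 | 0.71 | 0.57 | 0.31 | 0.21 | 0.12 |
| interview 15 | 0.97 | 0.87 | 0.50 | 0.31 | 0.18 |

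The last column compares A's share among the 20 − k respondents asked with B's share of all 20.

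**Step 3: chance of keeping a place.** Scoring below one rival is not the same as losing a place, so I also looked at the top five of ten themes. This was a simulation with 200,000 runs and ties broken at random. The late theme had a 60% rate when asked, and nine themes asked throughout had rates from 20% to 60% in steps of 5 points. Asked from the start, the late theme is kept with probability 0.95.

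| Question added after | Raw, q = 0% | Raw, q = 15% | Raw, q = 30% | Share of those asked |
|---|---|---|---|---|
| interview 5 | 0.69 | 0.78 | 0.85 | 0.93 |
| interview 10 | 0.16 | 0.42 | 0.67 | 0.89 |
| interview 15 | 0.00 | 0.11 | 0.43 | 0.80 |

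**The case against.** A reader might infer that a late-added barrier must score low, and that once dropped it is lost to the rest of the study. The documents support neither.

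- **Unprompted mentions count.** Interviews are semi-structured, and coding covers utterances, not only answers to guide questions. A theme that prompts a new question has probably already surfaced, which favours the higher unprompted rates. The expected count is reduced, not forced to be low.
- **Much refinement comes first.** "We will pilot provider interviews with study consultants", says Section 6, and a veteran council comments on the patient guide. The appendix list already contains two provider guides, and concurrent analysis depends on timing. No late addition is planned, although the wording about asking participants leaves it open.
- **Selection is not a mechanical cut-off.** Section 9 has the team discussing code summaries and memos, and lists themes with conflicting beliefs alongside frequent ones. That gives a second route, though only a partial one, because conflict is tallied on the same reduced exposure.
- **Later steps offer some recovery.** The DCE is pilot tested and revised on feedback (Section 7). Aim 1 also informs the pilot strategies directly, and the two Aim 3 strategies are already chosen in outline.
- **The calculation is a simplification.** The plan counts total mentions, with no limit per person, whereas the calculation caps them at one.
- **A share of those asked has its own weaknesses.** Themes are built from utterances, so some have no single related question. With k = 15 only five respondents have been asked, and a true 40% theme would then outrank a true 60% theme asked throughout with probability 0.18, against 0.07 at full exposure.

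These points limit the claim and shape the fix. They do not supply a rule for counting when exposure differs between themes.

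**Conclusion.** The point holds in a limited form. The plan permits the guide to change during fielding, scores themes by a total that ignores who was asked, and uses that score as one of two criteria for choosing DCE attributes. If a question is added during fielding, its theme may be under-ranked and left out of about five places. The direction is clear wherever asking raises mentions.

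The size is not fixed by the documents. For addition halfway through 20 provider interviews, the chance of mis-ranking against one weaker rival runs from 0.71 to 0.21 as the unprompted rate goes from 0% to 40%, against 0.07 with full exposure. An early addition with frequent unprompted mentions does little harm: in the top-five illustration, addition after interview 5 at a 30% unprompted rate keeps the theme with probability 0.85, against 0.95. All of this rests on assumed mention rates, assumed timing and one count per respondent. If no question is added or substantially changed, the problem does not arise.

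**What to change.** Keep the iterative guide. In Sections 6, 8 and 9, state the following.

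1. Record the guide version used for each interview.
2. Apply the final codebook to every transcript, early ones included, before counting.
3. Count respondents raising each theme, not total mentions.
4. For any theme whose question was added or substantially changed during fielding, show two figures: the share of all respondents, and the share of those interviewed with that guide version. Show unprompted mentions separately. Consider the theme for the DCE if it ranks high on either figure.
5. For themes with no specific question, use all respondents as the denominator.
6. Treat conflicting beliefs in the same way.

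The share of those asked should stand beside the all-respondent share and not replace it, given how few people a late question may reach.

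The cost is protocol wording, one variable per transcript, and some re-coding of at most 20 + 15 = 35 transcripts. The downside is that shares for late-added themes are imprecise, so ranking high on either figure will sometimes admit a weaker theme to consideration. Showing both denominators lets the team see when that is the case.

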1 BACKGROUND/SCIENTIFIC RATIONALE

A. BACKGROUND & SIGNIFICANCE

A1. Evidence for castration as prostate cancer treatment

Because prostate cancer cells are dependent on androgens, i.e., testosterone, depriving them of this hormone through castration can improve clinical outcomes, for some patients.¹ The highest levels of evidence for chemical castration with androgen deprivation therapy (ADT) injections to treat prostate cancer occur in two scenarios: 1) high risk localized disease in combination with radiation therapy, and 2) metastatic cancer with spread to bones or other organs causing symptoms.²⁻⁴ However, a significant amount of castration in Medicare and integrated delivery systems (e.g., VA), occurs outside scenarios where high levels of benefit exist.^{5,6} For example, using castration for the primary treatment of localized prostate cancer is likely ineffective and harmful, yet remains common in VA with five-fold variation across facilities (Figure 1). Neither long-term studies nor current guidelines support castration as primary treatment for localized prostate cancer.^{1,3,4} Many times, this castration is continued indefinitely. Even in cases of metastatic prostate cancer without symptoms, an American Society of Clinical Oncology Panel could not make a recommendation for treatment with ADT until symptoms of disease progression (e.g., bone pain) occur due to a lack of an overall survival advantage for those treated early.⁷

A2. There is a disconnect between the value and use of castration in prostate cancer

A2.1 *Surgery to remove testicles is no longer needed for castration*

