value ADT use in clinically localized prostate cancer. We plan to retrospectively analyze data from VA facilities across the United States to determine what facility level factors are associated with low value ADT use in clinically localized prostate cancer. We hypothesize that academic affiliation will be associated with higher value prostate cancer care. More broadly, this work can begin to fill knowledge gaps regarding academic affiliations and the value of specialty care delivery in VA.

Using national VA CDW, workforce (VSSC), and Central Cancer Registry data, we will analyze rates of ADT use in localized prostate cancer for VA facilities from 2016-2017. We will separate facilities into quartiles of low value ADT use and use regression models to identify those factors associated with higher value prostate cancer care (e.g., urologist workforce, resident number, hospital size, medical school affiliation, region). We will also examine the extent to which changes in low value ADT use over time are associated with changes in facility level characteristics. To better understand the influence of facility level factors on low value specialty care, we will identify facilities that changed quartiles of low value ADT use over the study period. We will then identify changes in facility factors associated with corresponding changes in low value ADT use using regression models. For example, if loss of urologist workforce was associated with increasing low value care this may inform strategies to proactively engage facilities facing specialty care recruitment challenges. This information could potentially inform development of Aims 2 and 3 of our study.

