7 DATA COLLECTION AND MANAGEMENT PROCEDURES

AIM 1: Only data from VA databases will be collected for participant identification and screening purposes. This data will be collected by the VA study data manager.

PROVIDERS:

For the semi-structured provider interviews, we will sample up to 20 VHA urologists from VHA facilities with the highest and lowest use of castration as primary treatment. We will use preliminary data from [name] CDA but then update the data using CDW Oncology data for the years 2016 and 2017 once our DART application is approved. We are also applying for access to Medicare claims data from VA Information Resource Center (VIReC) to validate we are not missing unidentified treatment with surgery or radiation therapy outside VHA. We plan to pull Medicare data on up to 20,000 patients. We will identify Urology Chiefs at each site using lists of providers from the most recent Federal Practitioner directory and national urologist email listserv. If possible, we will use CDW data to identify providers who meet the criteria of having experience caring for patients on ADT.

PATIENTS

We will use VA cancer registry data for years 2016 and 2017 to identify patients at high outlier sites on primary ADT for prostate cancer. Patients will be ineligible if they have dementia or other significant mental impairment noted in their medical record.

ACCESS TO DATA:

All identifiers, including interview recordings, will be stored in access restricted folders on VA servers behind the VA firewall. Only key study team members added to the AAVA IRB approved protocol personnel list will have access to data files containing PHI/PII. All personal identifiers will be stripped from the written verbatim transcripts of the interviews. Subjects will be instructed at the start of the interview to refrain from mentioning names of colleagues or from identifying the medical center.

DATA SAFETY MONITORING PLAN (DSMP):

[name] will be responsible for reporting all adverse events that might arise during the course of the study to the University of Michigan and the Ann Arbor Veterans Affairs Health System IRB. Adverse Events during this study would likely consist only of breaches in confidentiality. The following precautions have been taken to prevent this. However, should such breaches occur, [name] will report these occurrences to the overseeing IRBs within 48 hours.

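### Aim 4 marks change by moves between quartiles and does not say that rate change at all facilities is modelled; quartile-based change analyses lose power for modest effects

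*Combined protocol and SAP*

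**What the plan says.** The analysis plan for Aim 4 is in Section 6. Section 7 covers only data handling for this aim, Section 8 covers Aims 1 and 2, and Section 10 covers the pilot outcomes.

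Section 6 proceeds in this order:

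- Data: "we will analyze rates of ADT use in localized prostate cancer for VA facilities from 2016-2017".
- Factor analysis: "We will separate facilities into quartiles of low value ADT use and use regression models to identify those factors" linked to higher-value care.
- Change, as a general objective: "We will also examine the extent to which changes in low value ADT use over time are associated with changes in facility level characteristics".
- Change, as a procedure: "we will identify facilities that changed quartiles of low value ADT use over the study period".
- Change regression: "We will then identify changes in facility factors associated with corresponding changes in low value ADT use using regression models".

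The quartile is the only grouping named, and a move between quartiles is the only concrete marker of change. The dependent variable, the link function, any weighting for facility volume and the set of facilities in the change model are not stated.

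**The concern.** Three analyses fit this text:

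1. The quartile shift is itself the outcome.
2. Facilities that moved quartile are picked out first, and their rate changes are then modelled.
3. Rate change is modelled at all facilities, and quartiles only describe.

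The first discards the size of each change and treats a small facility like a large one. The second drops the non-movers. Because it selects facilities on the outcome, it also inflates the estimated effect. The third has neither problem, but the plan does not commit to it.

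At stake is whether a modest real link, such as loss of urologists followed by more low-value ADT, would be found. The list of facilities that changed is also meant to show how facility factors influence low-value care. If most moves come from sampling noise, that list is a poor guide.

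**Working it through.** Aim 4 gives no facility count, effect size or power, so there is no figure of the plan's own to reproduce. The analyses were compared by simulation.

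**Inputs tied to the documents**

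- Period: 2016-2017 (Section 6), taken as one rate per facility per year.
- Spread: Section 1 (A1) says that castration as primary treatment for localized disease "remains common in VA with five-fold variation across facilities". The percentiles are not given. Read as a 95th/5th or 90th/10th percentile ratio, this is an SD of 0.54-0.77 on the log-odds scale.
- Volume: Section 7 says, for Aim 1, "We plan to pull Medicare data on up to 20,000 patients". If that covered all men in both years, 20,000/2/130 = 77 and 20,000/2/100 = 100 men per facility-year. Half of 77, about 38, is the low value. The 20,000 is a ceiling for an Aim 1 check, so it is only a rough guide.

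**Assumed inputs**

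100-130 facilities; mean rate 10-20%; coefficient of variation of facility volume 0.6; unexplained drift SD 0.15 on the log-odds; a factor that changes at 20% of facilities; odds ratio (OR) 1.4; two-sided 0.05 (Section 8 states 0.05 for Aim 2 only).

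**Model**

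Counts are binomial. In year 1, logit(p) = μ + a. In year 2, logit(p) = μ + a + x·ln(OR) + d. Here a is the facility effect, d the drift, and x = 1 where the factor changed.

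**Chance moves**

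Take a facility with a true rate of 15% and 77 men. The standard error of one year's rate is √(0.15 × 0.85/77) = 4.1 points, and of the difference between years 4.1 × √2 = 5.8 points. With a median of 15% and SD 0.54, the middle half of true rates lies within ±0.674 × 0.54 = ±0.364 log-odds, or about 11% to 20%. The two middle quartiles are then about 4 and 5 points wide, no wider than the noise in the difference. In simulation with no true change, 39-62% of facilities changed quartile. A second simulation with other inputs gave 55-63%.

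**Power of the change analysis, lead setting (130 facilities, 77 men, 15% rate, OR 1.4)**

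| Analysis | Power | Loss against rate change |
|---|---|---|
| Quartile shift, all facilities | 65% | 80 − 65 = 15 points |
| Rate change, movers only | 70% | 80 − 70 = 10 points |
| Rate change, all facilities, unweighted | 80% | – |
| Binomial count model, all facilities | 88% | gain of 8 points |

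Repeat simulations of this setting gave 56-63%, 61-68% and 77-82% for the first three rows.

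Across eight settings, quartile shift had 30-68% power against 38-85% for unweighted rate change, a loss of 8-23 points. Movers only lost 5-16 points and overstated the effect by 29-43%. Varying the drift SD from 0 to 0.3 lowers the smallest losses to 6 and 3 points. The count model adds 6-13 points over unweighted rate change, mostly from volume weighting: volume-weighted rate change came within about 1.5 points of it.

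**Second simulation (log-odds SD 0.5, factor change at 25% of facilities)**

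| Facilities × men per year | OR | Rate change | Quartile shift | Loss (points) |
|---|---|---|---|---|
| 130 × 80 | 1.5 | 91.3% | 75.5% | 15.8 |
| 130 × 30 | 1.5 | 61.2% | 47.7% | 13.5 |
| 80 × 30 | 1.5 | 43.5% | 33.1% | 10.4 |
| 130 × 80 | 2.0 | 100% | 99.5% | 0.5 |
| 80 × 30 | 2.0 | 88.1% | 72.5% | 15.6 |

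The direction also held with 60 facilities, 15 men per year or a 6% mean rate. This simulation's movers-only test compared up with down moves, so it does not check the overstatement figure.

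**Type I error.** Null rejection in the change analysis was 4.6-7.8% across methods in the first simulation and about 4-6.5% in the second.

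**Academic affiliation (cross-sectional, OR 0.7, 60-80% affiliated).** A quartile score of 1-4 lost about 0-4 points against unweighted rates. In the second simulation (OR 1.3, 130 facilities) power was 66% for rates and 62% for the score, but 44% for top quartile yes/no.

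**The case against.** The strongest reply is that the text does not require a quartile outcome. The aim is introduced as an analysis of rates. The general objective on change mentions neither quartiles nor movers, and the closing regression refers to changes in use, not changes in quartile. The quartile step can be read as a supplement. This stands in part: the loss applies only if quartile shift or the movers are what is analysed. It does not remove the point, because the procedure selects quartile movers and only then turns to the corresponding changes, and no sentence commits to rate change at all facilities.

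It is also fair that nearly every input is assumed, so the ranges show likely size and are not precise. The whole gap to the count model should not be charged to quartiles either, since much of it comes from volume weighting, which the plan neither adopts nor excludes.

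A reader might infer more than this:

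- That Aim 4 will certainly be analysed on quartile shift. The wording leaves this open.
- That false-positive findings would rise. Null rejection stayed near 5% for quartile and rate methods alike.
- That the academic-affiliation hypothesis, the one hypothesis stated for this aim, is undermined. With quartiles scored 1-4 it is little affected.

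**Conclusion.** The point holds as a conditional loss of efficiency in the change analysis. It is not an error in any stated figure. At OR 1.4, with 100-130 facilities, 38-100 men per facility-year and a 10-20% mean rate, the loss against rate change at all facilities is roughly 8-23 points for quartile shift and 5-16 for movers only. The movers-only effect is about 30-40% too large. About 40-60% of facilities would change quartile with no true change, so a list of changed facilities would largely reflect noise.

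At OR 2.0 the loss is negligible in large settings but can reach about 15 points with small facilities. The direction did not depend on the assumed inputs; the size does. Stakes are limited, because Aim 4 is exploratory, has no power target, and is described only as possibly informing Aims 2 and 3. It is an improvement worth making, with medium confidence.

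**What to change.** In the Aim 4 text of Section 6:

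- Name the outcome as facility-year counts or rates of low-value ADT, modelled with facility volume taken into account. Use either a binomial (logistic) model with a facility random intercept or volume-weighted rate change.
- Fit the change model to all facilities, with a year term and the within-facility change in each factor.
- Keep quartiles and quartile moves for description only.

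The cost is slightly more analysis work. It uses data already planned and needs no new participants or data collection. If the team already intends to model rate change at all facilities, the edit puts that in writing and adds the allowance for volume.
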